3.6. End of Study

End of Study is defined as when the last subject has completed 52 weeks of dosing plus the 4 week post treatment visit or has entered the LTE.

¹ In each case, there is a need for additional investigations, such as review of ethanol, recreational drug and dietary supplement consumption; testing for acute hepatitis A, B or C infection and biliary tract imaging should be promptly discussed with the study Medical Monitor

3.7. Post Study Care

All subjects who meet criteria for clinical response (per protocol), and who complete 52 weeks of study assessments will be offered an opportunity to participate in a LTE study (GS-US-417-0304). Subjects who discontinue early from the main study, or switch to standard of care treatment during the study, are not eligible for the LTE. The long term care of subjects who do not qualify for the LTE or choose not to participate in the LTE will remain the responsibility of their primary treating physician.

3.8. Biomarker Samples

3.8.1. Biomarker Samples to Address the Study Objectives:

The following biological specimens will be collected in this study which may be used to evaluate the association of exploratory systemic and/or tissue specific biomarkers with study drug response, including efficacy and/or adverse events, and help inform the mechanism of action and mechanism of intrinsic and acquired resistance to filgotinib in RA. The specific samples to be collected from all subjects (unless otherwise stated) include the following:

- Plasma, serum, and urine samples for potential analysis of circulating factors including but not limited to cytokines, metabolome, biomarkers of joint damage, and miRNA
- Paxgene blood samples for potential gene expression analyses

- Whole blood sample for potential B-/T-cell receptor sequencing
- Viably frozen PBMCs (vfPBMCs) and Leukocyte subsets to profile immune cell subsets and inflammatory signaling pathways

The biomarker sample collection schedule is described in Study Procedures Table ([Appendix 2](#)). Since biomarker science is a rapidly evolving area of investigation, it is not possible to specify prospectively all tests that may be performed on the specimens collected. The testing outlined above is based upon the current state of scientific knowledge. It may be modified during or after the end of the study to remove tests no longer indicated and/or to add new parameters based upon the growing state of art knowledge. Any future testing of new tests not described above must be approved by local authorities as applicable according to specific local regulations.

The biomarker samples will be destroyed no later than 15 years after the end of study unless the subject gives specific consent for the remainder of the samples to be stored for optional future research.

For sampling procedures, storage conditions, and shipment instructions, see the Sample Handling and Logistics Manual.

3.8.2. Biomarker Samples for Optional Future Research

CCI [Redacted]

[Redacted]

[Redacted]

CCI [Redacted]

[Redacted]

[Redacted]

[Redacted]

CCI [Redacted]

CCI [Redacted]

[Redacted]

[Redacted]

[Redacted]

[Redacted]

CCI [Redacted]

[Redacted]

[Redacted]

4. SUBJECT POPULATION

4.1. Number of Subjects and Subject Selection

A sufficient number of subjects will be screened to ensure that approximately 1200 subjects with moderately to severely active RA will be randomized to one of 4 dosing groups.

4.2. Inclusion Criteria

Subjects must meet all of the following inclusion criteria to be eligible for participation in this study.

- 1) Male or female subjects who are ≥ 18 years of age, on the day of signing informed consent.
- 2) Have a diagnosis of RA (2010 ACR/EULAR criteria) ([Appendix 8](#)), and are ACR functional class I-III
- 3) Have ≥ 6 swollen joints (from a SJC66) and ≥ 6 tender joints (from a TJC68) at both Screening and Day 1 (need not be the same joints) ([Appendix 7](#))
- 4) Must meet at least one of the following parameters at Screening:
 - ≥ 1 documented joint erosion on radiographs of the hands, wrists or feet by central reading
 - OR
 - positivity for either RF or anti-CCP Ab (based on central laboratory)
 - OR
 - Serum CRP ≥ 4 mg/L (based on central laboratory)
- 5) Have limited or no prior treatment with MTX, ie, no more than 3 doses of MTX ≤ 25 mg each in the subject's lifetime for the treatment of RA, with the last dose at least 28 days prior to Day 1, and are an appropriate candidate for MTX therapy, as per investigator judgment
- 6) Females of childbearing potential (as defined in [Appendix 5](#)) must have a negative pregnancy test at Screening and Day 1
- 7) Male subjects and female subjects of childbearing potential who engage in heterosexual intercourse must agree to use protocol specified method(s) of contraception as described in [Appendix 5](#)
- 8) Lactating female subjects must agree to discontinue nursing from Screening through the end of their study participation.

9) Meet one of the following tuberculosis (TB) Screening criteria:

a) No evidence of active or latent TB:

- A negative QuantiFERON[®] TB-Gold In-Tube test at Screening and
- A chest radiograph (views as per local guidelines) taken at Screening or within the 3 months prior to Screening (with the report or films available for investigator review) without evidence of active or latent TB infection and
- No history of either untreated or inadequately treated latent or active TB infection

b) Previously treated for TB: ie, if a subject has previously received an adequate course of therapy as per local standard of care for either latent TB (9 months of isoniazid in a location where rates of primary multi-drug resistant TB infections are <5% or an acceptable alternative regimen) or active TB (acceptable multi-drug regimen). In these cases, no QuantiFERON[®] TB-Gold In-Tube test (or equivalent assay) need be obtained, but a chest radiograph must be obtained if not done so within 3 months prior to Screening (with the report or films available for investigator review). It is the responsibility of the investigator to verify the adequacy of previous anti-tuberculosis treatment and provide appropriate documentation.

c) Newly identified latent TB during Screening: ie, a subject who has a newly identified positive diagnostic TB test result (defined as a positive QuantiFERON[®] TB Gold in Tube test [or equivalent assay]) in which active TB has been ruled out and for which appropriate, ongoing, prophylactic treatment for latent tuberculosis has been initiated prior to the first administration of study medication. Adequate treatment for latent TB is defined according to local country guidelines for immunocompromised subjects.

Cases falling under category “b” and “c” need to be approved by the Sponsor prior to enrollment in the study. No subject with currently ACTIVE TB may be enrolled in the study, regardless of past or present anti-TB medication use.

10) Able and willing to sign the informed consent as approved by the IEC/IRB. Written consent must be provided before initiating any screening evaluations. Subjects must have read and understood the informed consent form (ICF), must fully understand the requirements of the trial, and must be willing to comply with all trial visits and assessments; subjects who cannot read or understand the ICF may not be enrolled by a guardian or any other individual.

11) Subjects receiving non-prohibited medication for any reason should be on a stable dose (defined as no change in prescription) within 7 days or 5 half-lives (whichever is longer) prior to the first administration of study drug on Day 1.

4.3. Exclusion Criteria

Subjects who meet *any* of the following exclusion criteria are not to be enrolled in this study.

1) Prior treatments for RA as follows:

- a) Alkylating agents, eg, chlorambucil or cyclophosphamide, at any time
- b) Previous treatment with any JAK inhibitor
- c) Previous therapy with csDMARDs other than MTX or hydroxychloroquine (eg, gold salts, cyclosporine, leflunomide, azathioprine, sulfasalazine or any other immunosuppressive).

NOTE: Subjects with prior exposure to csDMARD may be enrolled if the subject had limited exposure (less than 3 months of total exposure). Washout periods need to be satisfied per protocol (section 5.4).

- d) Use of any licensed or investigational biologic DMARDs (eg, B-cell depleting agents, tumor necrosis factor (TNF) alpha inhibitors, and/or interleukin (IL)-1, IL-6, IL-17, IL-12/23 inhibitors, including but not limited to abatacept, anakinra, certolizumab pegol, etanercept, golimumab, infliximab, rituximab, secukinumab, ustekinumab or tocilizumab
- 2) Known hypersensitivity or allergy to study drug, its metabolites, or formulation excipients.
 - 3) Known hypersensitivity or allergy to the MTX, its metabolites, or formulation excipients.
 - 4) Oral steroids at a dose >10 mg/day of prednisone (or equivalent) or a prescription for oral steroids which has changed within 4 weeks of Day 1.
 - 5) Receipt of an intra-articular or other injectable corticosteroid within 4 weeks prior to Day 1.
 - 6) Use of nonsteroidal anti-inflammatory drugs (NSAIDs) which have not been at a stable dose (defined as no change in prescription) for at least 2 weeks prior to Day 1. NOTE: subjects are permitted to take acetylsalicylic acid at a dose of ≤ 325 mg daily for cardiac prophylaxis, or occasional NSAIDs for non-RA indications (eg, headache).
 - 7) Administration of a live/attenuated vaccine within 30 days from Day 1, or planned during the study.
 - 8) Participation in any clinical study of an investigational drug/device within 4 weeks or 5 half-lives prior to Screening, whichever is longer. Exposure to investigational biologics are excluded as outlined in 1d.
 - 9) Have undergone surgical treatments for RA, including synovectomy or arthroplasty in >4 joints

- 10) Have any chronic, uncontrolled medical condition, which would put the subject at increased risk during study participation, such as uncontrolled: diabetes, hypertension, morbid obesity, thyroid, adrenal, pulmonary, hepatic, renal, neurologic or psychiatric disease, or other disease of concern, as per judgment of investigator.
- 11) Have a history of major surgery (requiring regional block or general anesthesia) within the last 3 months prior to Screening or planned major surgery during the study.
- 12) Have a moderately to severely active, generalized musculoskeletal disorder that would interfere with assessment of study parameters or increase risk to the subject by participating in the study, eg, generalized osteoarthritis, systemic inflammatory condition other than RA such as, but not limited to: ankylosing spondylitis, reactive arthritis, psoriatic arthritis, inflammatory bowel disease associated arthropathies, systemic lupus erythematosus, scleroderma, inflammatory myopathy, mixed connective tissue disease, overlap syndrome, or gout. Subjects with any history of Felty's syndrome or juvenile idiopathic arthritis are excluded, regardless of the disease activity level at Screening. (NOTE: subjects with concurrent Sjogren's syndrome or limited cutaneous vasculitis associated with RA are not excluded, and may be enrolled, based on investigator judgment).
- 13) Active autoimmune disease other than those listed above, that would interfere with assessment of study parameters or increase risk to the subject by participating in the study, eg, inflammatory bowel disease, uncontrolled thyroiditis, systemic vasculitis, transverse myelitis or uveitis.
- 14) Any known condition or contraindication as addressed in the local labeling or local clinical practice for MTX that would preclude the subject from participating in this study.
- 15) History of or current moderate to severe congestive heart failure (NYHA class III or IV), or within the last 6 months, a cerebrovascular accident, myocardial infarction, unstable angina, unstable arrhythmia new or significant ECG finding at Screening, or any other cardiovascular condition which, in the opinion of the Investigator, would put the subject at risk by participation in the protocol.
- 16) History of malignancy within the past 5 years prior to Screening (except for adequately treated basal cell carcinoma or non-metastatic squamous cell carcinoma of the skin or cervical carcinoma in situ with no evidence of recurrence).
- 17) History of lymphoproliferative disease or current lymphoproliferative disease.
- 18) History of gastrointestinal perforation.
- 19) History of organ or bone marrow transplant.
- 20) Positive serology for human immunodeficiency virus (HIV) 1 or 2.

- 21) Evidence of active Hepatitis C Virus (HCV) infection. Subjects with positive HCVAb at screening, require reflex testing for HCV RNA. Subjects with positive Hep C RNA viral load (VL) at screening will be excluded. Subjects with positive HCV Ab, but negative HCV RNA VL are eligible per investigator judgment, but require ongoing monitoring as outlined in the schedule of assessments. Subject with active HCV during the study, as evidenced by RNA positivity will be discontinued from study drug as outlined in the protocol.
- 22) Evidence of active Hepatitis B Virus (HBV) infection. Subjects with positive HBV surface antigen (HBsAg) at screening are excluded from the study. Subjects with positive HBV core Ab and negative HBsAg, require reflex testing for HBV DNA. Subjects with positive HBV DNA at screening will be excluded. Subjects with positive HBV core Ab, and negative HBV DNA are eligible per investigator judgment, but may require prophylactic treatment in accordance with HBV treatment guidelines/local standard of care and require ongoing monitoring with blood tests for HBV DNA every 3 months, as outlined in the schedule of assessments. Subject with evidence of active Hepatitis B during the study, as evidenced by DNA positivity, will be discontinued from study drug as outlined in the protocol.
- 23) History of opportunistic infection or immunodeficiency syndrome which would put the subject at risk, as per investigator judgment.
- 24) Active infection that is clinically significant, as per judgment of the investigator, or any infection requiring hospitalization or treatment with intravenous anti-infectives within 60 days of Screening; or any infection requiring oral anti-infective therapy within 30 days of Screening.
- 25) Currently on any therapy for chronic infection (such as pneumocystis, cytomegalovirus, herpes zoster, and atypical mycobacteria). Past history of disseminated staphylococcus aureus or disseminated Herpes simplex infection.
- 26) History of symptomatic herpes zoster within 12 weeks prior to Screening or have history of disseminated/complicated herpes zoster infection (multi dermatomal involvement, ophthalmic zoster, central nervous system involvement or postherpetic neuralgia)
- 27) History of an infected joint prosthesis or other implanted device with retention of the prosthesis or device in situ.
- 28) Current drug, tobacco or alcohol abuse, per investigator judgment.
- 29) Any condition including active fibromyalgia that based on the investigator's opinion would make it difficult to appropriately assess RA activity for the purposes of this study.
- 30) Any condition or circumstances which in the opinion of the Investigator or Sponsor may make a subject unlikely or unable to complete the study or comply with study procedures and requirements.
- 31) Use of prohibited medication as outlined in section [5.4](#)

- 32) Significant blood loss (>450 mL) or transfusion of blood product within 12 weeks prior to Day 1.
- 33) Tests performed at the central laboratory at Screening that meet any of the criteria below (out of range lab values may be rechecked one time, after consultation with the sponsor or its designee, before subject is considered a screen-failure):
- a) Hemoglobin <8.0 g/dL (International System of Units [SI]: <80 g/L);
 - b) White blood cells < 3.0×10^3 cells/mm³ (SI: < 3.0×10^9 cells/L);
 - c) Neutrophils < 1.5×10^3 cells/mm³ (SI: < 1.5×10^9 cells/L);
 - d) Lymphocytes < 0.5×10^3 cells/mm³ (SI: < 0.5×10^9 cells/L);
 - e) Platelets < 100×10^3 cells/mm³ (SI: < 100×10^9 cells/L);
 - f) Alanine aminotransferase (ALT) or aspartate aminotransferase (AST) ≥ 1.5 x ULN;
 - g) Total bilirubin level ≥ 2 x ULN unless the subject has been diagnosed with Gilbert's disease and this is clearly documented;
 - h) Estimated creatinine clearance <40 mL/min based on the Cockcroft-Gault formula.

CCI

[REDACTED]

[REDACTED]

[REDACTED]

[REDACTED]

[REDACTED]

[REDACTED]

CCI

[REDACTED]

CCI [REDACTED]
[REDACTED]
[REDACTED]

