On-treatment assessments will include: adverse events (AEs), concomitant medications, review of study medication compliance through drug accountability, SJC66, TJC68, Subject's Global Assessment, Subject's Pain Assessment, HAQ-DI, Functional Assessment of Chronic Illness Therapy-Fatigue (FACIT-Fatigue), Short-Form Health Survey (SF-36), Work Productivity and Activity Impairment- Rheumatoid Arthritis (WPAI-RA), EuroQol 5 Dimensions (EQ-5D), CCI [REDACTED] Treatment Satisfaction Questionnaire for Medication (TSQM), Healthcare Resource Utilization, Physician's Global Assessment, physical examination, weight, vital signs, serum CRP, blood and urine sampling for safety laboratory tests and biomarkers at selected visits, and urine pregnancy tests (females of child bearing potential only).

A resting 12-lead ECG should be performed at Screening, Weeks 12, 24, 36, and 52 or ET, and at the Post-treatment Week 4 follow-up visit. ECGs should be interpreted by the investigator (or qualified designee) for clinical significance.

For all subjects, blood samples for PK analysis should be collected at least 30 minutes post study drug dose on Week 4, prior to study drug administration on Weeks 12 and 24, and any time at the final assessment visit on Week 52 or ET.

CCI [REDACTED]

Blood samples for biomarker analysis should be collected at Day 1, Weeks 4, 8, 12, 24, 36, and Week 52 or ET and urine samples should be collected at Day 1, Weeks 12, 24, and Week 52 or ET.

Radiographs of the bilateral hands, wrists, and feet should be taken at Screening, Week 24, and Week 52 or ET. However, if a subject prematurely discontinues study participation and has had X-rays performed within the previous 12 weeks, then X-rays do not need to be repeated at the ET visit. Radiographs performed after enrollment may be done +/-7 days of the scheduled visit.

Post treatment follow-up assessments include AEs, concomitant medications, physical examination, 12-lead ECG, weight, vital signs, blood and urine sampling for safety laboratory tests, and urine pregnancy tests (females of child bearing potential only).

CCI

[REDACTED]

Test Product, Dose, and Mode of Administration:	200 mg filgotinib orally q.d. plus MTX weekly up to 20 mg 100 mg filgotinib orally q.d. plus MTX weekly up to 20 mg 200 mg filgotinib orally q.d.
--	---

Reference Therapy, Dose, and Mode of Administration:	MTX weekly up to 20 mg or PTM MTX weekly PTM filgotinib 200 mg orally q.d. PTM filgotinib 100 mg orally q.d.
---	--

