6.7. Study Assessments

6.7.1. Efficacy

Efficacy assessments will be carried out at Day 1 and at Weeks 2, 4, 8, 12, 16, 20, 24, 30, 36, 44, and 52, or at ET (if applicable).

Assessments of RA will include the derived ACR (ACR20, 50, 70 as well as ACR-N and EULAR response criteria, DAS28 [CRP], CDAI, and SDAI as well as the individual components of the ACR response criteria [TJC68, SJC66], HAQ-DI, Physician's Global assessment, Subject's Global Assessment, Subject's Assessment of Arthritis Pain and CRP]) and radiographs of hands, wrists and feet (mTSS and mTSS components of erosion score and joint space narrowing).

Additionally, subjects will be asked to complete questionnaires, including the FACIT-Fatigue scale, SF-36, EQ-5D, TSQM, WPAI-RA at Day 1 and at Weeks 4, 12, 24, 36, and 52, or at ET (if applicable). Healthcare resource utilization will be assessed at the Day 1 and at Weeks 12, 24, 36 and 52, or at ET (if applicable).

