6.7.3. Clinical Laboratory Evaluations

The hematology and serum chemistry laboratory analyses will be performed at a central laboratory. Reference ranges will be supplied by the central laboratory and will be used by the investigator to assess the laboratory data for clinical significance and pathological changes.

Blood samples will be collected by venipuncture **CCI** in the arm at the time points indicated in the study procedures table ([Appendix 2](#)). In addition, urine samples for the clinical laboratory assessments will be collected. Subjects only need to be fasted at days where lipid profiling is scheduled.

Please refer to [Appendix 6](#) for table of Clinical laboratory tests.

The laboratory values outside the normal range will be flagged and clinical relevance will be assessed by the investigator. More frequent sampling as well as additional tests may be performed as deemed necessary by the investigator as indicated.

Note that in the case where clinically significant laboratory test results are a potential reason for discontinuation from the study drug and withdrawal from the study, retesting of the affected parameter(s) should be prompt (within 3 to 7 days) after the investigator has consulted with the medical monitor. A decision regarding subject discontinuation should be made after the results from the retest are available (see [Section 3.5](#) for additional information).

The details of sample handling and shipment instructions will be provided in a separate laboratory manual.

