Serology	X ^r														
Viral Monitoring ^s						X			X		X		X		

[figure not shown]
EVENT		Screening ^a	Treatment Period											Follow-Up ^d	
Visits			Day 1 ^b	W2	W4	W8	W12	W16	W20	W24	W30	W36	W44	W52/ ET ^c	Post Treatment Week 4
Visit window (Days)				(±3 days)	(±3 days)	(±3 days)	(±3 days)	(±3 days)	(±3 days)	(±3 days)	(±7 days)	(±7 days)	(±7 days)	(±7 days)	(±7 days)
Imaging ^e	Hand, Wrist and Feet Radiographs ^t	X							X				X		
	CCI														
Assessment of Adverse Events		X	X	X	X	X	X	X	X	X	X	X	X	X	
Concomitant Medications		X	X	X	X	X	X	X	X	X	X	X	X	X	
Randomization/reassignment			X						X ^v		X ^w	X ^w	X ^w		
Study Drugs Dispensation ^x			X		X	X	X	X	X	X	X	X			
Review entry criteria for LTE (if applicable)													X		

Footnotes

- a Screening window is 28 days prior to Day 1, the window may be extended to up to 42 days prior to the Day 1 visit for subjects who require repeat collection of radiographs
- b Subject will begin study drugs on Day 1, following baseline assessments and randomization.
- c Early Termination Visit to be performed if subject discontinues before Week 52
- d The follow-up visit will be performed only for subjects discontinuing prematurely from the study and for those completing Week 52 but not entering the LTE.
- e Eligibility criteria check based on the laboratory results from the Screening visit, TJC/SJC at screening and Day 1 and for female subjects of childbearing potential, the urine pregnancy test at Day 1.
- f Medical History includes smoking status, average weekly alcohol consumption, family history of coronary heart disease and any other chronic medical conditions or prior surgeries
- g At Screening, Week 24 and Week 52 (or at ET), a complete physical should be performed. Symptom driven exams should be performed at all other visits. Height will be measured at Screening only.
- h Chest X-ray for TB assessment should be performed unless performed in the previous 3 months, with results available at the site.
- i Subject reported outcomes are recommended to be performed first at each visit prior to any other visit-related procedures (other than signing of informed consent), as much as possible. Questionnaire translations will be provided to subjects when and where available.
- j Vital signs are defined as heart rate, respiratory rate, blood pressure (systolic and diastolic) and body temperature.

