- k For female subjects of childbearing potential only. To be performed on serum sample at Screening and on urine samples for other visits. For female subjects entering the LTE, at the Week 52 visit pregnancy test should be performed on serum. During the periods where visits are every 6-8 weeks, women should continue to have monthly home pregnancy tests performed at home. The site will call the subject every 4 weeks to obtain results of these pregnancy tests. If any pregnancy test is positive, study drug should be immediately interrupted and subject should come to the site for serum pregnancy test.
- l Refer to list provided in Laboratory assessment table ([Appendix 6](#)).
- m Urine samples for biomarker analysis should be collected at Day 1, Weeks 12, 24, and Week 52 or ET
[REDACTED]
- n The PK sample at Week 4 should be collected at least 30 minutes post study drug dose in the clinic. PK samples at Week 12 and Week 24 should be collected prior to study drug dose (within 2 hours prior to dosing). The PK sample at Week 52 or ET can be collected at any time during the visit. **CCI**
[REDACTED]
- p Details of biomarker collection are outlined in lab manual
- q Only for subjects in United States and Canada
- r Hepatitis B surface Ag and core Ab, reflex Hep B DNA, Hepatitis C Ab, reflex HCV RNA, HIV 1 and 2 at Screening.
- s Viral monitoring for HBV or HCV as applicable (see Exclusion criteria, Section 4.3).
- t Radiographs performed after enrollment may be done +/- 7 days of the scheduled visit. If subject discontinues study early and has had x-rays in the <12 weeks prior, x-rays do not need to be repeated at the ET visit.
[REDACTED]
- v Subjects failing to achieve at least a 20% improvement from Day 1 in TJC and SJC will discontinue study drugs, but will continue with study visits and assessments
- w Subjects failing to maintain at least a 20% improvement from Day 1 in TJC and SJC (confirmed at 2 consecutive visits) will discontinue study drugs, but will continue with study visits and assessments
- x Dispensation of study drugs according to IWRS manual.

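### Minor text-versus-schedule mismatch: HBV DNA testing is required every 3 months, but the schedule, best read as Weeks 12, 24, 36 and 52, leaves 112 days from Week 36 to Week 52

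*Protocol*

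**What the plan says.** Criterion 22 in Protocol Section 4.3 lets core antibody-positive, DNA-negative subjects enter at the investigator's judgment. They "may require prophylactic treatment in accordance with HBV treatment guidelines/local standard of care", and they "require ongoing monitoring with blood tests for HBV DNA every 3 months, as outlined in the schedule of assessments". Criterion 21, the parallel rule for HCV, asks for ongoing monitoring but gives no interval, so the 3-month figure applies to HBV only.

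The schedule is Appendix 2. Its Viral Monitoring row carries footnote s: "Viral monitoring for HBV or HCV as applicable (see Exclusion criteria, Section 4.3". The footnote gives no frequency of its own and sends the reader back to the criterion. The pre-dose test is in the Serology row, whose footnote r reads "Hepatitis B surface Ag and core Ab, reflex Hep B DNA, Hepatitis C Ab, reflex HCV RNA, HIV 1 and 2 at Screening". Sections 6.4 and 6.5, which list the assessments by visit in running text, do not mention viral monitoring.

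Under Section 3.5.2, HBV DNA positivity during the study is a reason to stop study drug permanently. Dosing lasts up to 52 weeks (Section 3.4).

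**The concern.** The criterion sets a number and names the schedule as the place where it is carried out. If the schedule tests at Weeks 12, 24, 36 and 52, the first three intervals are 12 weeks and the last is 16. A site that follows the table then departs from the criterion in the last third of treatment.

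DNA positivity by itself triggers the stop; no rise in transaminases is needed. The Week 52 result comes when in-study dosing ends, so Week 36 is the last scheduled DNA test that can stop dosing within the study. The subject at stake is one who turns DNA-positive after Week 36 without an ALT or AST rise and is still on drug. That subject's next scheduled test comes about 3 weeks later than the criterion allows.

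**Working it through.** **1. Which visits the row marks.** Counting cells after the row label as 1 Screening, 2 Day 1, 3 Week 2, 4 Week 4, 5 Week 8, 6 Week 12, 7 Week 16, 8 Week 20, 9 Week 24, 10 Week 30, 11 Week 36, 12 Week 44, 13 Week 52/ET and 14 Post Treatment, the Viral Monitoring marks stand in cells 6, 9, 11 and 13. Three rows with known weeks check this count:

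- Serology, the adjacent row, has its only mark in cell 1. Footnote r places it at Screening.
- Healthcare Resource Utilization/TSQM has marks in cells 2, 6, 9, 11 and 13. Section 6.7.1 says "Healthcare resource utilization will be assessed at the Day 1 and at Weeks 12, 24, 36 and 52".
- Biomarker blood samples have marks in cells 2, 4, 5, 6, 9, 11 and 13. The Synopsis says "Blood samples for biomarker analysis should be collected at Day 1, Weeks 4, 8, 12, 24, 36, and Week 52 or ET".

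The Viral Monitoring marks are therefore best read as Weeks 12, 24, 36 and 52.

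**2. The intervals.** Nominal days come from SAP Section 4.2.1: Week 12 = Day 85, Week 24 = Day 169, Week 36 = Day 253, Week 44 = Day 309, Week 52 = Day 365. Windows in Appendix 2 are ±3 days at Weeks 12 and 24 and ±7 days at Weeks 36, 44 and 52. Three months is taken as 365/4 = 91 days.

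| Interval | Nominal days | With windows | Nominal minus 91 |
|---|---|---|---|
| Day 1 to Week 12 | 85 − 1 = 84 | 81 to 87 | −7 |
| Week 12 to Week 24 | 169 − 85 = 84 | 78 to 90 | −7 |
| Week 24 to Week 36 | 253 − 169 = 84 | 74 to 94 | −7 |
| Week 36 to Week 52 | 365 − 253 = 112 | 98 to 126 | +21 |

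The excess in the last interval ranges from 98 − 91 = 7 to 126 − 91 = 35 days, so it is over 3 months even at its shortest.

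**3. If the row were displaced by one column.**

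- True weeks 8, 20, 30 and 44: the longest interval is Week 30 to Week 44, 14 × 7 = 98 days (84 to 112 with windows). It is nominally 7 days over, but could comply within the windows.
- Displaced the other way, true weeks 16, 30, 44 and Post Treatment: the first interval alone is 16 × 7 = 112 days.

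**4. With a Week 44 test added.** Week 36 to Week 44 is 309 − 253 = 56 days, and Week 44 to Week 52 is 365 − 309 = 56 days (42 to 70 each with windows). The nominal on-drug intervals become 84, 84, 84, 56 and 56 days.

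**5. What that leaves.** Screening may be up to 28 days before Day 1, or 42 if radiographs are repeated. From the Screening test to a nominal Week 12 visit is then up to 28 + 84 = 112 days, or 42 + 84 = 126 days.

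**The case against.** The strongest objection is to the evidence. The finding rests on one blank cell in a table that came through PDF text extraction damaged. The ECG, quantitative immunoglobulin, lipid and radiograph rows are displaced. The CRP, hematology/chemistry, pregnancy and adverse event rows have lost marks. The drug dispensation row has no Week 44 mark although dosing continues to Week 52. In the adverse event, concomitant medication and dispensation rows, Screening falls in the second cell after the label; the same offset here would give Weeks 8, 20, 30 and 44. No running text states the viral monitoring weeks. This objection stands as a reason to check the source table before changing anything. It does not overturn the reading: the adjacent Serology row contradicts the offset, and the Weeks 8/20/30/44 alternative still has a nominal 98-day interval.

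Second, the criterion sets no maximum interval and defers to the schedule, and four tests in 52 weeks average one per 13 weeks. It is true that 91 days is not a hard limit. But an average does not turn a single 16-week interval into 3-monthly testing, and footnote s sends the reader back to the criterion for the rule.

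Third, there are safeguards. Transaminases are drawn at Week 44, the hepatic stopping rules and hepatitis work-up of Section 3.5.2 apply, prophylaxis is possible, and under Section 6.7.3 "More frequent sampling as well as additional tests may be performed as deemed necessary by the investigator as indicated". The Week 52 result can still inform entry to the extension study. All of this stands and makes the residual risk small. None of it is a scheduled DNA test between Weeks 36 and 52.

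A reader might infer that HBV reactivation goes unwatched for 16 weeks. The safeguards above show that it does not.

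**Conclusion.** The point holds as a minor mismatch between criterion 22 and the schedule. On the best reading of the table, the last on-drug HBV DNA interval is 112 days (98 to 126) against about 91, some 3 weeks over. It rests on two assumptions: that the marks fall at Weeks 12, 24, 36 and 52, and that the Week 44 cell is blank in the source table. The first is well supported; the second cannot be settled from the extracted text.

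Only core antibody-positive subjects still on drug after Week 36 are affected, and the documents do not give their number. No endpoint, alpha or power is touched.

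Two stronger readings should be avoided. One is that the plan certainly omits a Week 44 test; a damaged table cannot show that. The other is that a Week 44 test would bring the whole study within 3 months test to test. It would mend the on-drug schedule counted from first dose, but the interval from the Screening test to Week 12 would remain as long as 112 or 126 days.

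**What to change.** First check the Week 44 cell of the Viral Monitoring row in the source table. If it is marked, nothing needs to change. If it is blank, and the other marks are confirmed at Weeks 12, 24, 36 and 52, add an HBV DNA test at Week 44 for core antibody-positive subjects still on drug. Week 44 is the only scheduled visit between Weeks 36 and 52, so no new visit is needed.

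The cost is one mark in the table and at most one extra assay per such subject, at a visit where blood is already drawn. If the sponsor means the 3 months to run from the Screening test rather than from first dose, that needs a separate decision; this change does not address it.
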